#### **13.1.4.5 Penn Physician Withdrawal Checklist**

Descriptive summaries (mean, SD, median, minimum, and maximum) will be presented for scores from the PWC-20 checklist, completed at Visits 14 and 15.

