2.2. Study Endpoints

2.2.1. Safety Endpoints

The safety endpoints of this study include the following:

- Incidence and severity of AEs, AEs leading to discontinuation, and SAEs
- Changes in vital signs results
- Changes in clinical laboratory evaluation (hematology, chemistry, and urinalysis) results
- Changes in 12-lead ECG results
- Changes in physical examination findings
- Changes in HAM-D17 scores
- Changes in C-SSRS scores
- PWC-20 scores after termination of PH94B

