7.5. Exploratory Efficacy Analysis

All exploratory endpoints will be summarized for descriptive purposes only.

The following variables will be summarized for all subjects completing each visit. All derived variables will be computed as described in Section 0.

Categorical data will report frequency of responses and proportion of responders by study visit:

1. Proportion of CGI-I responders will be assessed from Visit 3 to Visit 14 by study visit.
2. Change in proportion of PGI-C responders will be assessed from Visit 3 to Visit 14 by study visit.
3. Proportion of CGI-S scores > 4 by from Visit 2 to Visit 14 by study visit.

Continuous data will report descriptive statistics of observed values and change from baseline by study visit:

4. Change in LSAS total scores by visit.
5. [REDACTED]

8. Safety and Tolerability Analysis

Safety in this study will be evaluated based on data collected on AEs, clinical laboratory assessments, vital signs, 12-lead ECGs, PWC-20 (at Visit 14/15 End of Study/Follow-up), and physical examinations including examination of the nasal passages. As a precautionary measure, subjects will also be assessed using the C-SSRS and HAM-D at each study Visit.

All safety analysis reporting will be based on the Safety Population (as defined in Section **Error! Reference source not found.**). No formal statistical testing will be conducted for the safety analyses. Descriptive statistics will be used to evaluate safety data. Summaries will present data by overall subjects. Listings will list safety data by subject.

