8.1. Adverse Events

Treatment emergent AEs (TEAEs) are defined as:

- AEs with onset at the time of or following the start of treatment with IP through final Visit or follow-up phone call.
- AEs starting prior to the start of treatment with IP but increasing in severity or relationship at the time of, or following, the start of treatment with IP through Visit 14 (End of Treatment/Follow-Up).
- AEs that occur between Visit 14 and Visit 15.

Any medical condition that is present at the time that the subject is screened will be considered as baseline and not reported as an AE. However, if the study subject's condition deteriorates at any time during the study, it will be recorded as an AE.

The Investigator will record all reportable events with start dates occurring any time after informed consent is obtained until 7 days after the last day of study participation. Events will be followed for outcome information until resolution or stabilization. Missing and partially missing start dates will be imputed for the purpose of analysis as described in Section **Error! Reference source not found.**

All AEs, TEAEs, and serious AEs (SAEs) will be coded using the MedDRA dictionary, as discussed in Section **Error! Reference source not found.**

All AE data will be categorized as Severe > Moderate > Mild. Relationship of all AEs to IP will be categorized as related or not related. In the summaries showing severity and relationship to study drug, the event with the maximum severity or strongest relationship to study drug will be reported. If a particular event is missing the severity and/or relationship, then the strongest possible severity or relationship will be assumed for analysis (severity = severe, relationship = related).

An overall summary of TEAEs will be provided; this will present number and percent of subjects who reported at least 1 of the following: TEAE (including any TEAE, TEAEs by maximum severity, and related TEAEs), TEAE leading to discontinuation of the study drug, TEAE leading to discontinuation from the study, serious TEAEs, and SAEs leading to death. TEAEs will be summarized by two time periods (TEAEs which occur prior to Visit 14 and those that occur during or after Visit 14).

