In addition to the overall summary, summaries of the number and percentage of subjects with TEAEs will be displayed by overall by SOC and preferred term by time period. Summaries of TEAEs by severity (Severe > Moderate > Mild) and relationship to IP (Related > Not Related)

will also be provided. Serious TEAEs and TEAEs resulting in discontinuation of IP will be summarized separately in a similar manner.

Subject listings of AEs, SAEs, and AEs causing discontinuation of IP will be produced. Adverse events that are treatment emergent will be flagged.

The AE summary tables will include counts of subjects. Therefore, if a subject experiences more than 1 episode of a particular AE, the subject will be counted only once for that event. If a subject has more than 1 AE that is coded to the same preferred term, the subject will be counted only once for that preferred term. Similarly, if a subject has more than 1 AE within a SOC, the subject will be counted only once in that SOC. This will be handled separately for each time period (post-Visit 2 through Visit 15 [End of Treatment/Follow-up]).

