8.7. Penn Physician Withdrawal Checklist

The PWC-20 consists of 20 questions related to withdrawal from benzodiazepines or other anti-anxiety compounds. The symptoms measured are based on those that are potentially related to anxiolytic withdrawal: gastrointestinal, mood, sleep, motor, somatic, perception, and cognition. The questions will cover any symptoms that might occur during the week following discontinuation of PH94B.

Summaries of PWC-20 total scores and frequency and percentage of subjects with withdrawal symptoms will be presented overall for only those subjects who completed both Visit 14 and Visit 15. Descriptive statistics for total scores and frequencies of withdrawal symptoms will be presented by Visit 1 and Visit 15.

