16.2 Subject Data Listings		
Listing 16.2.9.3	All Enrolled Subjects	Physical Examination Measurements
Listing 16.2.9.4	All Enrolled Subjects	Quick Olfactory Test (QOT)
Listing 16.2.9.5	All Enrolled Subjects	Prior and Concomitant Medications
Listing 16.2.9.6	All Enrolled Subjects	Columbia Suicide Severity Rating Scale (C-SSRS) Screening
Listing 16.2.9.7	All Enrolled Subjects	Hamilton Depression Rating Scale (HAM-D)
[REDACTED]	[REDACTED]	[REDACTED]
Listing 16.2.9.9	Subects with Visit 14 and Visit 15	Physician Withdrawal Checklist (PWC-20)
[REDACTED]	[REDACTED]	[REDACTED]

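### SAP 8.7 names Visit 1 for the PWC-20, an evident slip for Visit 14; once corrected, the supplied text still describes only pooled visit-wise summaries and no count of symptoms new at Visit 15

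*SAP*

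**What the plan says.** SAP 8.7 restricts the PWC-20 summary to a paired set, "presented overall for only those subjects who completed both Visit 14 and Visit 15", and then says: "Descriptive statistics for total scores and frequencies of withdrawal symptoms will be presented by Visit 1 and Visit 15".

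Every other reference places the checklist at the last two visits. The opening of SAP section 8 has "PWC-20 (at Visit 14/15 End of Study/Follow-up", and Protocol 13.1.4.5 plans descriptive summaries of "scores from the PWC-20 checklist, completed at Visits 14 and 15". Both schedules of events, and Protocol 10.2.3 and 10.2.4, mark it at Visit 14/ET and Visit 15 only.

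The safety endpoint in SAP 2.2.1 is "PWC-20 scores after termination of PH94B". Withdrawal symptoms are also part of the primary objective in Protocol 6.1. SAP 2.1.1 leaves them out, but the endpoint itself is kept.

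The planned outputs are one table (14.5.3, population Safety) and one listing (16.2.9.9), whose population is "Subects with Visit 14 and Visit 15".

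**The concern.** The visit label is wrong as printed, and correcting it does not complete the analysis. The question the checklist is meant to help with is whether symptoms appear after PH94B is stopped. That is a within-subject question, and two separate visit-wise percentages do not answer it.

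Elsewhere the SAP does describe within-subject measures for its safety data: treatment-emergent ideation and behavior for the C-SSRS (8.6), change from baseline for the HAM-D (8.8), and change with 95% confidence intervals for laboratory values (8.2). For the one instrument directed at withdrawal, none is described.

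Pooling adds to the difficulty. For a completer, treatment concludes at Visit 14. An early stopper has a visit with the same number, held after stopping or at the visit where stopping is decided. The same column therefore describes different positions relative to the last dose. In addition, a subject who completes the checklist at Visit 14/ET and misses Visit 15 appears in neither the 8.7 summary nor the PWC-20 listing.

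**Working it through.** The documents give no rate, sample size or precision for the PWC-20, so there is no planned figure to reproduce.

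**1. Visit label.** Both schedules, Protocol 10.2.3, 10.2.4 and 13.1.4.5, SAP section 8 and the preceding sentence of SAP 8.7 all point to Visits 14 and 15. No PWC-20 exists at Visit 1. The only consistent reading is Visit 14.

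**2. What is described after correction.** SAP 8.7 and Protocol 13.1.4.5 give summaries of scores by visit; SAP 8.7 adds symptom frequencies. Neither mentions a change or a cross-classification of the two visits.

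**3. Who is in the Visit 14 column.**
- Completers: treatment concludes at Visit 14 (Protocol 7.1).
- Early stoppers: seen as soon as possible after discontinuing (Protocol 7.1), or assessed at a scheduled visit where the decision to stop is made (Protocol 10.2.3).
- Analysis visits follow the nominal label (SAP 6.1.5) and safety summaries are for subjects overall (SAP section 8), so nothing described separates these groups.

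**4. What visit-wise percentages can show.** In the paired set, let a be the proportion symptomatic at both visits, b at Visit 14 only and c at Visit 15 only. Then p14 = a + b and p15 = a + c. The quantity of interest is c, and the two percentages only bound it:

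max(0, p15 − p14) ≤ c ≤ min(p15, 1 − p14).

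With p14 = p15 = p, this becomes 0 ≤ c ≤ min(p, 1 − p), which is 0 to p when p is at most 50%. For an assumed p = 20%, the lower bound is max(0, 0.20 − 0.20) = 0 and the upper bound is min(0.20, 0.80) = 0.20. So 20% at both visits could mean that nobody, or up to 20% of subjects, became newly symptomatic. The bound does not depend on the number of subjects.

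**5. Total score.** Because the set is paired, the mean change equals the difference of the two visit means. Its precision does not follow from the two visit-wise SDs, since it also depends on the within-subject correlation.

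**6. Listing.** SAP 6.1.8 says everything collected will be listed. Listing 16.2.9.9 requires both visits. A single PWC-20 is collected data that this filter excludes.

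**The case against.** **The plan meets its own endpoint.** The endpoint is worded as scores, and Protocol 13.1.4.5 asks only for descriptive summaries at Visits 14 and 15. Protocol 7.1 does list withdrawal symptoms among items summarized through changes, but from Visit 2 to Visit 14, and the PWC-20 is not collected at Visit 2. This stands: the point is an improvement, not a departure from protocol.

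**The table shell was not supplied.** Table 14.5.3 may contain a change column. This stands and limits the claim to what the supplied text describes.

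**Other displays keep part of the information.** Clinically relevant observations at a visit count as AEs (Protocol 11.2.1). SAP 8.1 splits "TEAEs which occur prior to Visit 14 and those that occur during or after Visit 14", and these summaries "will be displayed by overall by SOC and preferred term by time period". Paired subjects' checklists are listed, so new symptoms could be found by hand. A reader might infer that post-stopping symptoms are lost altogether; the documents do not support that. What is missing from the description is a summary at checklist level.

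**The contrast is imperfect.** Protocol 10.3.1.2.5 and SAP 8.7 say the questions concern symptoms in the week after stopping. An early stopper may already have such symptoms at the ET visit, and a count of symptoms absent then and present at Visit 15 would miss them. Splitting by completion status also leaves both kinds of early stopper together. Time since last dose would be the better variable, but dose times come from the eDiary, which SAP section 10 calls unreliable. This objection stands, which is why the ET visit needs its own summary.

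**The size is hypothetical.** The upper bound requires every subject symptomatic at Visit 14 to recover while as many others become symptomatic. That is fair; the bound shows what the summary cannot exclude, not what is likely.

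**Conclusion.** The point holds and is minor. The Visit 1 label is an evident slip. A reader might infer that an empty or wrong table would follow, or that a screening PWC-20 was intended; the consistent placement at Visits 14 and 15 elsewhere rules out the second and makes the first implausible.

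After correction, the supplied text describes visit-wise results only, pooled over completers and early stoppers, in subjects with both visits. Equal percentages p at the two visits, with p at most 50%, then leave the newly symptomatic proportion anywhere from 0 to p. The bound is exact given the percentages, but any particular p is an assumption. The conflict between Listing 16.2.9.9 and SAP 6.1.8 stands on the text alone.

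Two limits apply. The unsupplied table shell may show more. And with as-needed dosing and a single arm, a change from Visit 14/ET to Visit 15 would describe what was observed; it would not be a clean or causal measure of withdrawal.

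**What to change.** In SAP 8.7:

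- Change Visit 1 to Visit 14/ET.
- For subjects with both assessments, add the change in total score (Visit 15 minus Visit 14/ET) with a descriptive 95% confidence interval.
- In the same subjects, add the number and percentage with symptoms present at Visit 15 but absent at Visit 14/ET.
- Show both separately for 12-month completers and early-termination subjects.
- For early-termination subjects, also report symptoms present at the ET visit itself, including subjects with no Visit 15, because the new-symptom count would miss symptoms that began after stopping but before ET.
- Report how many subjects have only one PWC-20, and extend Listing 16.2.9.9 to everyone with any PWC-20.
- State that the results are descriptive.

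The cost is SAP wording, one change score, one new-symptom flag and a wider listing filter, all from data already collected. The downside is minor programming and small subgroups, especially among early stoppers.

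As a side note, the documents time Visit 15 in three ways: 54 weeks ±3 days (schedules of events), about 2 weeks after the last administration (Protocol 7.1) and 2 weeks after the last visit (Protocol 10.1). These passages should be reconciled.

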8.8. Hamilton Depression Scale (HAM-D)

Total scores and change from baseline will be summarized for the Safety population.

8.9. Coronavirus 2019 (COVID-19) Impact

The SARS-CoV-2 virus and variants may still be a threat and safety precautions may still be in place during study enrollment. To assess the impact of the COVID-19 pandemic on study

AD-ST-33.06 Effective date: 12-Nov-2020

procedures, study staff will complete the COVID-19 Impact questionnaire. Should a study Visit be affected by COVID-19, study staff will record how the Visit was affected (missed, abbreviated, delayed, performed remotely, or otherwise deviating from the planned format in the protocol) and which procedures were impacted. All COVID-19 protocol deviations will be provided in a separate listing. This listing will include the subjects, affected Visits, and affected assessments.

10. Changes from Planned Analysis

Endpoints removed: analysis not performed – data not collected.

Study staff will complete the Coronavirus 2019 (COVID-19) Impact questionnaire to assess the impact of the COVID-19 pandemic on study procedures. The COVID-19 Impact questionnaire is described in Section [8.9](#). All COVID-19 protocol deviations will be provided in a separate listing.

Exploratory objectives (changes in pattern of PH94B use daily frequency and dosing interval) requiring the use of eDiary data were removed due to unreliability of eDiary data.

The original planned interim safety analysis was removed from the study.

A qualitative review of categorical data was done instead of an assessment of a change in proportion over time due to limited availability of data.

11. References

ASA. (2018) Ethical Guidelines for Statistical Practice. Prepared by the Committee on Professional Ethics, April 2018. <http://www.amstat.org/about/ethicalguidelines.cfm>

Carpenter JR and Kenward MG. *Multiple Imputation and its Application (Statistics in Practice)*. Chichester, West Sussex, UK: John Wiley & Sons; 2013.

Graham JW, and Olchowski AE, Gilreath TD. (2007) “How Many Imputations are Really Needed? Some Practical Clarifications of Multiple Imputation Theory.” *Prev Sci.* 2007;8(3): 206-213.

ICH (1998). ICH Harmonised Tripartite Guideline. Statistical Principles for Clinical Trials E9; 1998. https://database.ich.org/sites/default/files/E9_Guideline.pdf

Little R and Rubin D. (1987). Statistical Analysis with Missing Data, New York: Wiley.

RSS. (2014) The Royal Statistical Society: Code of Conduct, 2014. <https://rss.org.uk/about/policy-and-guidelines/code-of-conduct/>.

12. Tables, Listings, and Figures

All listings, tables, and graphs will have a header showing the sponsor company name and protocol and a footer showing the version of SAS, the file name and path, and the source of the

data (e.g., listing number).

The following are planned summary tables for protocol number PH94B-CL032. The table numbers and page numbers are place holders only and will be determined when the tables are produced.

The following are planned summary tables for protocol number <Protocol>. The table numbers and page numbers are place holders only and will be determined when the tables are produced.

12.1. Demographic Data Summary Tables and Figures

Table 3: Demographic Data Summary Tables and Figures

Table Number	Population	Table Title/Summary
14.1 Demographic Data Summary Tables and Figures		
Table 14.1.1.1	All Subjects	Subject Enrollment and Disposition
Table 14.1.1.2	All Subjects	Protocol Deviations
Table 14.1.2.1	Safety	Demographics and Baseline Characteristics
Table 14.1.3	Safety	Medical and Psychiatric History by System Organ Class and Preferred Term
Table 14.1.4	Safety	Prior Medications by ATC Class and Preferred Term
Table 14.1.5.1	Safety	Exposure to Investigational Product
Table 14.1.5.2	Safety	PH94B Use by Study Visit

12.2. Efficacy Data

12.3. Safety Data

Table 2: Safety Data

Table Number	Population	Table Title / Summary
14.3.1 Displays of Adverse Events		
Table 14.3.1.1	Safety	Overall Summary of Treatment Emergent Adverse Events
Table 14.3.1.2.1	Safety	Treatment Emergent Adverse Events by System Organ Class and Preferred Term
Table 14.3.1.2.2	Safety	Treatment Emergent Adverse Events by Preferred Term
Table 14.3.1.3	Safety	Treatment Emergent Adverse Events by System Organ Class, Preferred Term, and Maximum Severity

Table Number	Population	Table Title / Summary
Table 14.3.1.4	Safety	Treatment Emergent Adverse Events by System Organ Class, Preferred Term, and Maximum Relationship to Investigational Product
14.3.2 Summary of Deaths, Other Serious and Significant Adverse Events		
Table 14.3.2.1	Safety	Treatment Emergent Adverse Events Leading to Study Discontinuation by System Organ Class and Preferred Term
Table 14.3.2.2	Safety	Serious Treatment Emergent Adverse Events by System Organ Class and Preferred Term
Table 14.3.2.3	Safety	Serious Treatment Emergent Adverse Events Related to Investigational Product by System Organ Class and Preferred Term
14.3.3 Narratives of Deaths, Other Serious and Certain Other Significant Adverse Events		
Table 14.3.3.1	Safety	Subject Listing of Serious Adverse Events
Table 14.3.3.2	Safety	Subject Listing of Adverse Events Leading to Discontinuation of Investigational Product
Table 14.3.3.3	Safety	Subject Listing of Adverse Events Leading to Death
14.3.4 Abnormal Laboratory Values		
Table 14.3.4.1	Safety	Subject Listing of Abnormal Laboratory Values: Clinical Chemistry and Thyroid
Table 14.3.4.2	Safety	Subject Listing of Abnormal Laboratory Values: Hematology
Table 14.3.4.3	Safety	Subject Listing of Abnormal Laboratory Values: Urinalysis
14.3.5 Laboratory Data Summary Tables		
Table 14.3.5.1.1	Safety	Hematology: Observed Results and Change and Percent Change from Baseline by Study Visit
Table 14.3.5.1.2	Safety	Hematology: Shifts from Baseline Relative to the Normal Range
Table 14.3.5.2.1	Safety	Clinical Chemistry: Observed Results and Change from Baseline by Study Visit
Table 14.3.5.2.2	Safety	Clinical Chemistry: Shifts from Baseline Relative to the Normal Range by Study Visit
Table 14.3.5.3.1	Safety	Quantitative Urinalysis: Observed Results and Change from Baseline by Study Visit
Table 14.3.5.3.2	Safety	Quantitative and Qualitative Urinalysis: Shifts from Baseline Relative to the Normal Range
Table 14.3.5.3.3	Safety	Qualitative Urinalysis: Summary of Results by Study Visit
14.3.6 Other Safety Data Summary Tables		

Table Number	Population	Table Title / Summary
Table 14.3.6.1	Safety	Vital Signs: Observed Results and Change from Baseline by Study Visit
Table 14.3.6.2.1	Safety	12-Lead Electrocardiogram: Summary of 12-Lead Electrocardiogram Interpretation by Study Visit
Table 14.3.6.2.2	Safety	12-Lead Electrocardiogram: Summary of 12-Lead Electrocardiogram Interpretation by Study Visit
Table 14.3.6.2.3	Safety	12-Lead Electrocardiogram: Summary of QT and QTcF Results by Study Visit
Table 14.3.6.4	Safety	Summary of Concomitant Medications by ATC Class and Preferred Term
Table 14.3.6.5	Safety	Summary of Columbia Suicide Severity Rating Scale (C-SSRS) by Study Visit

12.4. Other Data Summary Tables

Table 5: Other Data Summary Tables

Table Number	Population	Table Title / Summary
14.5 Other Data Summary Tables		
Table 14.5.1	Safety	Hamilton Depression Scale (HAM-D): Observed Results and Change from Baseline by Study Visit
Table 14.5.3	Safety	Summary of Physician Withdrawal Checklist (PWC-20)

12.5. Planned Listing Descriptions

The following are planned data and patient/subject data listings for protocol number <Protocol>.

In general, one listing will be produced per CRF domain. All listings will be sorted by treatment, site, and subject number. All calculated variables will be included in the listings.

In all listings a blank line will be placed between each subject. Within a data listing, if an item appears line after line (eg, repetition of subject number), then only the first occurrence will be displayed.

In data listings, the information for one subject will be kept on one page if at all possible, rather than splitting a subject's information across pages.

Table 6: Planned Listings

Listing Number	Population	Listing Title / Summary
16.2 Subject Data Listings		
16.2.1 Subject Discontinuations/Completions		
Listing 16.2.1.1	All Enrolled Subjects	Subject Disposition
16.2.2 Protocol Deviations		
Listing 16.2.2.1	All Subjects	Inclusion and Exclusion Criteria
Listing 16.2.2.2	All Enrolled Subjects	Protocol Deviations
Listing 16.2.2.3	Screen Failures	Reasons for Screen Failures
